## e) Study Endpoints

**Primary Outcome:** Development of SSI within study follow-up period. **Secondary Outcomes:** Length of hospital stay and serious adverse events.

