## f) Procedures Involved in the Human Research

Subjects will be consented prior to each eligible surgery. Prior to surgery, each prospective subject will be interviewed by a member of the study team and a medical history will be obtained. Randomization will occur prior to the start of surgery. The subject will then undergo their scheduled surgery and if they are placed in the experimental arm, they will receive the negative pressure wound therapy. If the subject is in the control arm, they will receive the standard of care wound dressings. Post-operatively, each patient will be followed for up to 37 days and monitored for the development of an SSI and secondary outcomes. If there is no evidence of a wound infection by post-operative day 5, the NPWT device will be removed. A follow-up, outpatient assessment at 30 days ( $\pm$  7 days) post-operatively will be included for all patients who did not develop a SSI.

It is anticipated that approximately 2% or less of subjects enrolled into this study will require re-operation of the principal incision for within 5-7 days after the original surgery due to various life-threatening complications which may include bleeding, anastomotic dehiscence or other septic complications. For subjects requiring re-

	Protocol Title:	Prophylactic Negative Pressure Wound Therapy to Reduce Surgical Site Infections in Elective Clean-Contaminated Colon Resections
	Principal Investigator	[name]
	Name/Contact Info:	[name], [contact]
Mount	Primary Contact	[name]
Sinai	Name/Contact Info	[name], [contact]
	Date Revised:	10/10/2018
	Study Number:	

intervention, who did not develop an SSI prior to the reoperation, the NPWT device will be re-applied and the study period re-defined based on the latter procedure.

	Screening ≤ 30 days preop	Baseline	Day 1	Day 2	Day 3	Day 4	Day 5	Final Visit 23 to 37 days post op
Study Activity								
Informed Consent	X							
Enrollment Criteria	Х							
Demographic/ Clincal Information		X						
Medical History	Х							
Inclusion/Exclusion Criteria	Х							
Randomization		Х						
Surgery		Х						
Application of NPWT Device		Х						
Bloodwork	Х			X*			X*	
SSI Assessment		Х	Х	Х	Х	X	Х	Х
AE Monitoring	Х	Х	Х	Х	Х	Х	Х	Х
Concomitant Medications	Х	Х	Х	Х	Х	Х	Х	Х

Study schedule of events. \* indicates that study event may occur with 24 hours of study visit.

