#### **MSSM Principal Monitor:**

Principle Investigator:

First Name: [name] Last Name: [name] Academic Title: Clinical [name]: Surgery Mailing Address: [name] [contact] [contact] E-mail: [contact]

2. Justify your choice of principal monitor in terms of the assessed risk to the research subject's health and wellbeing. In high risk studies when the principal monitor is independent of the study staff, indicate the individual's credentials, relationship to the PI, and the rationale for selection. [name] is the PI of the study and

	Protocol Title:	Prophylactic Negative Pressure Wound Therapy to Reduce Surgical Site Infections in Elective Clean-Contaminated Colon Resections
	Principal Investigator Name/Contact Info:	[name] [name], [contact]
Mount Sinai	Primary Contact Name/Contact Info	[name] [name], [contact]
	Date Revised:	10/10/2018
	Study Number:	

designated principal monitor. He is a certified, accomplished colorectal surgeon with extensive clinical and research experience on colorectal operations and wound management.

3. List the specific items that will be monitored for safety: Adverse events

4. Indicate the frequency at which **ACCUMULATED** safety and data information: At least annually—more often depending on volume of enrollment.

6. Where applicable, indicate dose selection procedures that will be used to minimize toxicity: This is a phase 3 trial, so dosing ranges to minimize toxicity have already been established.

7. List any specialized grading system that will be used to evaluate adverse events: N/A

 8. Describe procedures that will be used to assure data accuracy and completeness: Periodic monitoring visits where the monitor will go through collected data, confirming with source documents the accuracy and completeness of the data.
9. Should a temporary or permanent suspension of your study occur, in addition to the PPHS, indicate to whom (NIH, FDA, sponsor, IRB) will you report the occurrence: IRB.

All serious adverse events (SAEs) will be reported to KCI Inc. within 24 hours of learning of the event. SAEs will be reported for the entire duration of the study protocol, up to 37 days post operation.

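### The reoperation rule restarts the study period after randomisation, and so moves the primary endpoint window, without saying which dressing or start date a reoperated control has

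*Combined protocol and SAP*

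**What the plan says.** All references are to the combined protocol and SAP.

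- **Section 5f (Procedures), reoperation.** The protocol expects that "approximately 2% or less of subjects enrolled into this study will require re-operation of the principal incision", within 5 to 7 days of the first operation, for life-threatening complications such as bleeding or anastomotic dehiscence. If such a patient had no SSI beforehand, "the NPWT device will be re-applied and the study period re-defined based on the latter procedure". The sentence speaks of subjects and names no arm.
- **Section 5f, control arm.** "If the subject is in the control arm, they will receive the standard of care wound dressings". Nothing is said about a control who is reoperated.
- **Section 5e (Study Endpoints).** The primary outcome is "Development of SSI within study follow-up period". Serious adverse events are a secondary outcome.
- **Section 1 (Objectives).** The question concerns incisional SSI in the 30 days following elective colorectal surgery.
- **Section 5d (Study Timelines).** Follow-up lasts at most 37 days from surgery. A restart is not mentioned.
- **Section 5i (Data and Safety Monitoring Plan).** "SAEs will be reported for the entire duration of the study protocol, up to 37 days post operation". Which operation is meant is not stated.
- **Section 5h (Data Management).** Descriptive, univariate and multivariate analyses are named. No analysis set or crossover rule is given.

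**The concern.** The primary outcome has no window of its own; it takes the study follow-up period. A rule that restarts that period therefore changes the endpoint for the patients concerned. The trigger occurs after randomisation and could be affected by treatment. The restart also depends on the patient being judged free of SSI before the reoperation, which is a judgement on the primary outcome itself.

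The rule is written as if every reoperated patient wore the device, yet 220 of the 330 planned patients are controls. Two people applying the text could give the same reoperated control different windows, or a different dressing. With no analysis set or crossover rule, the choice could be made after outcomes are known, in patients who may have a high risk of SSI. The restart also fits poorly with a question about 30 days from an elective operation, because an emergency reoperation is not that operation.

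**Working it through.** **1. Readings the text allows**

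| Reading | Window for reoperated NPWT patients | Window for reoperated controls | Dressing for reoperated controls |
|---|---|---|---|
| A. Rule covers NPWT patients only | restarted | from index operation | standard |
| B. Rule covers all subjects, taken literally | restarted | restarted | NPWT |
| C. Restart covers all; re-application only for those who had the device | restarted | restarted | standard |

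Under A the windows differ by arm. Under B controls cross over. Under C the arms are treated alike, but time zero still depends on an event after randomisation. No section chooses among them.

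**2. Patients affected** (section 5f ceiling of 2%; section 5c arm sizes)

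- Total: 0.02 × 330 = 6.6
- NPWT: 0.02 × 110 = 2.2
- Control: 0.02 × 220 = 4.4

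These are upper figures, since the protocol says 2% or less and patients with an SSI before reoperation fall outside the rule.

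**3. Shift of the window** (reoperation at day 5 to 7)

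- Restarted follow-up ends at 5 + 37 = day 42 to 7 + 37 = day 44 after the index operation, against day 37 without a restart: 5 to 7 days later.
- A 30-day window counted from the reoperation would end at 5 + 30 = day 35 to 7 + 30 = day 37, inside the original follow-up.

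**4. The plan's sample size, as a baseline for power**

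Inputs from section 5c: 25% against 12.5%, 220 and 110 patients, two-sided chi-square, 80% power. Alpha is not stated; I assume 0.05.

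- Arcsine formula: h = 2·asin(√0.25) − 2·asin(√0.125) = 0.3245. NPWT n = (1.960 + 0.842)² × 1.5 / h² = 111.8, so 112 and 336 in total, close to the stated 330.
- Pooled formula with an unweighted mean rate: 333.
- Usual pooled formula with a weighted mean rate: 354, with 77.2% power at 220/110.

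So 330 is reproduced within 3% by two standard variants.

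**5. Cost of reading B**

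Suppose all 2% of controls cross over and take the 12.5% rate. The control rate becomes 0.98 × 25% + 0.02 × 12.5% = 24.75%.

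| Method | Planned power | With crossover |
|---|---|---|
| Pooled | 77.2% | 75.7% |
| Exact Pearson | 77.7% | 76.1% |
| Arcsine | 79.3% | 77.9% |

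The loss is about 1.5 points.

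**6. Sensitivity of a result to two patients**

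Two NPWT patients are 2/110 = 1.8 points, against a planned difference of 12.5 points. Planned NPWT events are 0.125 × 110 = 13.75, about 14; planned control events are 0.25 × 220 = 55. By uncorrected chi-square against 55/220:

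- 14/110: p = 0.010; 16/110: p = 0.029. Adding two events to the planned count does not change significance.
- 16/110: p = 0.029; 18/110: p = 0.075. In a borderline trial it could.

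This illustrates a borderline case and is not a forecast. It would need nearly all of the 2.2 expected reoperated NPWT patients to have a first SSI in the extra 5 to 7 days.

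**The case against.** The strongest reply is that this is a wording gap with little consequence. Reading C is at least as natural as the others: the sentence names no arm, a device can be re-applied only to someone who had it, and each patient then keeps the assigned dressing. That stands. A reader might infer that the arms certainly get different windows or that controls certainly cross over; the text allows this but does not establish it.

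A reader might also infer that SAE reporting fails to follow the restart. Section 5i does not show that. Reporting for the whole study duration could follow a restarted period, while the 37-day limit could refer to either operation. The window is undefined. Only if it is tied to the index operation would the last 5 to 7 days of a restarted period be uncovered.

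It is also true that the rule erases no earlier SSI. It can change an outcome only for a first SSI that arises or is detected after the original window closes. A longer window for NPWT alone would add events to that arm, and crossover of controls to an effective device would lower the control rate, so readings A and B both work against the device. To say that the rule breaks the randomised comparison would be out of proportion.

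Finally, restarting the clock alike in both arms when the incision is reopened is a defensible choice, and the mismatch between a 30-day question and a 37-day follow-up exists without any reoperation. Both points are fair. They do not remove the need to fix one time origin in advance, and the plan does not do so for controls.

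**Conclusion.** The concern holds in a limited form. Section 5f makes the time origin of the primary endpoint depend on an event after randomisation, in wording that fits only the device arm, and leaves the dressing and window of reoperated controls unstated. Differential windows, crossover of controls and an SAE window that ignores the restart are possible readings, not established facts.

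The size is small: at most about 6.6 of 330 patients, a window 5 to 7 days later, and about 1.5 points of power even if every reoperated control crossed over. The case for change rests on a clear endpoint definition and comparability between arms, not on power. The figures assume the protocol's own 2% ceiling equally in both arms, reoperation at day 5 to 7, two-sided alpha of 0.05 and, for the crossover figure, a 12.5% SSI rate in controls given the device. A higher reoperation rate, or one that differs by arm, would enlarge the problem.

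**What to change.** For the primary analysis, state that the SSI window starts at the index operation for every randomised patient, that patients are analysed in the assigned arm, and that any incisional SSI in that window counts whether or not reoperation occurred. Report a restarted window only as a sensitivity analysis, applied identically to both arms. Record the date of SSI onset so that both windows can be derived.

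The downside is that an SSI first arising in the last 5 to 7 days of a restarted period is left out of the primary analysis; the sensitivity analysis would show it.

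Sections 5f and 5i must also be reconciled on what reoperated controls receive and on which operation starts the 37-day SAE period. Those choices are for the investigators. The analysis clock for SSI should not be used to shorten safety follow-up after a second operation; SAE comparisons need only use the same window in both arms.

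The cost is a few sentences of protocol text, with no added patients or procedures.

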#### g) Specimen Banking

N/A

## h) Data Management and Confidentiality

All research data for this study will be kept in individual patient research folders, which are locked in either a storage office on the storage of [name] or in the locked office of the research manager. In addition, data will be entered into the secure study database which will only be accessible by the research personnel. All patients will only be identified by a unique ID on all study related materials in patient research folders and on the database. The log linking ID numbers to patient identities will be kept in a password protected file on a Mount Sinai networked computer. The research manager, research coordinator, and investigators will have access to the file containing identifiers.

	Protocol Title:	Prophylactic Negative Pressure Wound Therapy to Reduce Surgical Site Infections in Elective Clean-Contaminated Colon Resections
	Principal Investigator Name/Contact Info:	[name] [name], [contact]
Mount Sinai	Primary Contact Name/Contact Info	[name] [name], [contact]
	Date Revised:	10/10/2018
	Study Number:	

The data and related publication will be stored according to MSSM's institutional guidelines. The principal investigator will keep the data on a mass storage device (example: Mount Sinai's server) for a minimum period of six years after publication. The study investigators will have access to the study data, which will be stored on a Mount Sinai secured, shared network drive. The de-identified data will be analyzed using statistical software that is installed on a secure Mount Sinai computer. Descriptive analysis and univariate tests will be performed. Logistic and linear multivariate analyses will also be run.

### i) Provisions to Monitor the Data to Ensure the Safety of subjects

#### Part I: Elements of a Data and Safety Monitoring Plan

1. List the name(s) of the individual(s) at MSSM who will be responsible for data and safety monitoring of this study. For each individual, indicate their role, name, title, and department information. The Principal Investigator may be the only monitor of a study.

If the qualifications of an individual to serve as a monitor are not contained in the PPHS application, they must be added to the DSMP either as a narrative description or as a CV.

#### **MSSM Principal Monitor:**

Principle Investigator:

First Name: [name] Last Name: [name] Academic Title: Clinical [name]: Surgery Mailing Address: [name] [contact] [contact] E-mail: [contact]

2. Justify your choice of principal monitor in terms of the assessed risk to the research subject's health and wellbeing. In high risk studies when the principal monitor is independent of the study staff, indicate the individual's credentials, relationship to the PI, and the rationale for selection. [name] is the PI of the study and

	Protocol Title:	Prophylactic Negative Pressure Wound Therapy to Reduce Surgical Site Infections in Elective Clean-Contaminated Colon Resections
	Principal Investigator Name/Contact Info:	[name] [name], [contact]
Mount Sinai	Primary Contact Name/Contact Info	[name] [name], [contact]
	Date Revised:	10/10/2018
	Study Number:	

designated principal monitor. He is a certified, accomplished colorectal surgeon with extensive clinical and research experience on colorectal operations and wound management.

3. List the specific items that will be monitored for safety: Adverse events

4. Indicate the frequency at which **ACCUMULATED** safety and data information: At least annually—more often depending on volume of enrollment.

6. Where applicable, indicate dose selection procedures that will be used to minimize toxicity: This is a phase 3 trial, so dosing ranges to minimize toxicity have already been established.

7. List any specialized grading system that will be used to evaluate adverse events: N/A

 8. Describe procedures that will be used to assure data accuracy and completeness: Periodic monitoring visits where the monitor will go through collected data, confirming with source documents the accuracy and completeness of the data.
9. Should a temporary or permanent suspension of your study occur, in addition to the PPHS, indicate to whom (NIH, FDA, sponsor, IRB) will you report the occurrence: IRB.

All serious adverse events (SAEs) will be reported to KCI Inc. within 24 hours of learning of the event. SAEs will be reported for the entire duration of the study protocol, up to 37 days post operation.

## j) Withdrawal of Subjects

Subjects may voluntarily withdraw from the study at any time without risk that their clinical care will be jeopardized in any way. Subjects wishing to withdraw must do so in writing to the principal investigator whose contact information will be provided on a copy of the informed consent document that has been signed by the participant and given to them to take home.

### 6) Risks to Subjects

1. There is the risk of loss of private health information; this risk always exists, but there are procedures in place to minimize the risk.

2. There is the risk of an adverse allergic reaction in patients who are allergic or hypersensitive to acrylic adhesives or silver.

3. There is a slight possibility that NPWT device could cause local wound erythema and irritation.

	Protocol Title:	Prophylactic Negative Pressure Wound Therapy to Reduce Surgical Site Infections in Elective Clean-Contaminated Colon Resections
	Principal Investigator Name/Contact Info:	[name] [name], [contact]
Mount Sinai	Primary Contact Name/Contact Info	[name] [name], [contact]
	Date Revised:	10/10/2018
	Study Number:	

The following AEs are theoretically possible following the application of NPWT device. If reported these events should be considered as unexpected:

- (1) Hypersensitivity or inflammatory reaction to surfaces of the device.
- (2) The risks to unborn or nursing (breast-feeding) infants are unknown. The NPWT device, although unlikely, may be hazardous to unborn or nursing infants.

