### Brief Summary of Research (250-400 words):

The purpose of this study is to see if the Negative Pressure Wound Therapy (NPWT) system is effective and safe for the prevention of superficial and deep incisional surgical site infections (SSI) in high risk patients within 30 days after elective colorectal surgery. It has been shown that patients with an IBD, patients undergoing a reoperation or patients with certain comorbidities are at a higher risk of developing an SSI. The NPWT device is a wound dressing with a vacuum system that can be placed over abdominal wounds. The study will include up to 400 patients at this single site, where these high risk patients will be randomized to receive either one of two arms. The first arm involves the placement of the NPWT device in the immediate postoperative period over abdominal wounds after clean-contaminated and contaminated colorectal surgical procedures. The device would then be left on for 5 days. The second arm would be standard of care and would entail routine postoperative protocols. Subjects will then be seen once at a 30 day ( $\pm$  7 days) follow-up visit to assess for the development of SSIs.

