## 5) Study Design

## a) Recruitment Methods

The research coordinator and the investigators will screen the office schedules of the investigators for patients presenting for clean/contaminated colorectal surgeries. A HIPAA waiver was submitted to the IRB to allow the study coordinator to access names, telephone numbers, and medical record numbers (MRN) to inform an investigator of the patient's potential eligibility. Other PHI identifiers have the potential to be seen since the pre-screening does involve opening the electronic medical records of these patients. However, the study team is only specifically looking for elements of PHI that would help them to determine eligibility and be able to identify the patient for consenting (name, MRN, date of birth, date of surgery). After identifying the possible patient, the investigator will approach the patient about the study, to see if the patient is interested. If the patient's office visit or prior

	Protocol Title:	Prophylactic Negative Pressure Wound Therapy to Reduce Surgical Site Infections in Elective Clean-Contaminated Colon Resections
	Principal Investigator Name/Contact Info:	[name] [name], [contact]
Mount Sinai	Primary Contact Name/Contact Info	[name] [name], [contact]
	Date Revised:	10/10/2018
	Study Number:	

to a scheduled screening visit. The patient will not be considered enrolled until it is determined that they have met all inclusion criteria and do not meet any exclusion criteria the day of the procedure.

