## b) Inclusion and Exclusion Criteria

All patients from aged 18 or older who will undergo an open or laparoscopicassisted clean-contaminated or contaminated colorectal surgical procedure will be included if they meet the following criteria. Patients must either have an inflammatory bowel disease, undergoing a stoma reversal, undergoing reoperation within 30 days, or have two or more of the following risk factors: presence of an ostomy, creation of an ostomy, type II diabetes, BMI greater than 30, immunosuppression, malnutrition, current smoker, chronic kidney disease (creatinine > 1.2), and disseminated cancer. Exclusions include patients currently enrolled in another interventional clinical trial, patients with a current infection (including a known urinary tract infection), patients allergic to or hypersensitive to silver, patients planning to undergo a second colorectal surgical procedure (e.g., colostomy or ileostomy takedown) or any other general surgery in less than 30 days of index-surgery, any patient in which the planned surgery would include: i) placement of a stoma in the principal incision; ii) placement of a drain into the supra-peritoneal fascia space that emerges through the principal incision; iv) placement of a drain into the intraperitoneal space that emerges through the principal incision; and v) supplementation of any of the irrigation fluid with antibiotic or antiseptic drugs, patients with healing disorders, pregnant women, prisoners, or any patient that is deemed unsuitable for the study by the Principal Investigator or the operating surgeon/Co-Investigator.

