## c) Number of Subjects

Up to 400 subjects are expected to be consented at this site. A series of 330 high risk patients undergoing elective, open or laparoscopic-assisted, clean contaminated cases involving colon resection will be enrolled in this study, of which 110 patients will receive an intraoperative application of NPWT and 220 control patients will receive the standard of care. This number was chosen based on a power analysis. Assuming the NPWT group will have a 50% reduction from the current clean-contaminated colon resection SSI rate of approximately 25%, a two-sided, chi-square power analysis indicated that with a 2:1, control to experimental ratio, 330 total subjects will be needed to detect this difference with 80% power. This number was rounded up to a

	Protocol Title:	Prophylactic Negative Pressure Wound Therapy to Reduce Surgical Site Infections in Elective Clean-Contaminated Colon Resections
	Principal Investigator	[name]
	Name/Contact Info:	[name], [contact]
Mount	Primary Contact	[name]
Sinai	Name/Contact Info	[name], [contact]
	Date Revised:	10/10/2018
	Study Number:	

total of 400 patients expected to be consented in order to account for screen failures, changes in operative and post-operative treatments, and subjects lost to follow-up. These patients will be allocated to each study arm using a simple randomization scheme. Mount Sinai performed almost 1,000 clean-contaminated colon resections in 2015, and we believe the proposed study can be completed in less than 2 years from the first enrollment.

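### Acrylic-adhesive allergy is named as a device risk in Section 6 but is not an exclusion in Section 5b, which covers silver allergy only

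*Combined protocol and SAP*

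**What the plan says.** Section 6 (Risks to Subjects), item 2, gives a single risk for two materials: "There is the risk of an adverse allergic reaction in patients who are allergic or hypersensitive to acrylic adhesives or silver". The same section lists, among theoretically possible events to be treated as unexpected if reported, "Hypersensitivity or inflammatory reaction to surfaces of the device".

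The only allergy exclusion in Section 5b (Inclusion and Exclusion Criteria) is "patients allergic to or hypersensitive to silver". The list closes with a discretionary clause covering "any patient that is deemed unsuitable for the study by the Principal Investigator or the operating surgeon/Co-Investigator".

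Under Section 5a (Recruitment Methods), a patient counts as enrolled only once it is established that "they have met all inclusion criteria and do not meet any exclusion criteria the day of the procedure". Section 5f (Procedures) provides that before surgery "each prospective subject will be interviewed by a member of the study team and a medical history will be obtained", and places randomisation before surgery starts. On the wear time in the NPWT arm, the Brief Summary says: "The device would then be left on for 5 days".

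**The concern.** The protocol identifies two groups as being at risk of an allergic reaction to the device and keeps only one of them out by rule. A patient with a known acrylic-adhesive allergy passes the enrolment check as written and, if allocated to NPWT, would wear the device over a fresh incision for 5 days.

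What is at stake is patient safety, not inference. Silver-allergic patients are protected by a stated criterion. Adhesive-allergic patients depend on someone asking about the allergy, recording it and acting on it. Two other provisions add weight. Section 7 bills treatment of device-related injury to the patient's insurance. Section 5i makes the Principal Investigator the safety monitor, with accumulated data reviewed at least once a year. Keeping a known risk out at entry is more dependable than detecting it later.

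**Working it through.** The plan has no figure to reproduce on this point, so the main check is a comparison of the text.

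| Material | Named as an allergy risk (Section 6, item 2) | Named exclusion (Section 5b) |
|---|---|---|
| Silver | Yes | Yes |
| Acrylic adhesives | Yes | No |

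1. Section 6 is the only place where acrylic adhesives appear. Section 14 (Vulnerable Populations) adds exclusions but none for allergy.
2. The check in Section 5a refers to the listed criteria. An unlisted allergy does not fail it, so the patient is eligible unless someone uses the discretionary clause.
3. That clause would also reach silver allergy, yet silver has its own rule. Discretion alone was evidently not thought enough for one of two materials that Section 6 puts in the same sentence.

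The size can only be scaled. Inputs from Section 5c (Number of Subjects): 400 consented, 330 enrolled, 110 allocated to NPWT. Allergy prevalence *p* is not given, so 0.5% to 5% is an assumption used to show a range.

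- Chance that an enrolled patient receives the device: 110 / 330 = 1 in 3.
- Exposed NPWT patients without the exclusion: at most 110 × *p*.
- Extra screen failures with the exclusion: at most 400 × *p*.
- Allowance between consent and enrolment: 400 − 330 = 70, and 70 / 400 = 17.5%.

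| Assumed *p* | Exposed, 110 × *p* | Screen failures, 400 × *p* |
|---|---|---|
| 0.5% | 0.55 | 2 |
| 1% | 1.1 | 4 |
| 2% | 2.2 | 8 |
| 5% | 5.5 | 20 |

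Both columns are upper bounds for the given *p*. The exposure column assumes that discretion removes nobody. The screen-failure column assumes that every affected patient is found only after consent, although the record review in Section 5a could find some earlier.

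**The case against.** The strongest case on the other side accepts the mismatch and disputes its weight.

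- **A disclosed risk need not become an exclusion.** Section 6 also mentions a possible hazard to nursing infants, while Section 5b excludes pregnant women but not nursing women. The two sections are therefore not matched item by item, and the sponsor may have meant to leave adhesive allergy to clinical judgement. This is possible, but no such intention is stated, and the nursing example may be a second omission.
- **There are several safeguards.** Investigators will have read the protocol (Section 4), records are opened at pre-screening (Section 5a), a history is taken (Section 5f), risks are discussed at consent (Section 12), and subjects may withdraw at any time (Section 5j). Adverse events are monitored at baseline and on each of Days 1 to 5, the period of wear. This stands as mitigation: a careful surgeon would probably exclude many such patients, and a reaction would arise under daily observation. But none of these steps names adhesive allergy or requires exclusion, and monitoring acts only after exposure.
- **The added harm is not quantified.** Section 6 gives no severity for the reaction, and the make-up of the control dressings is not stated, so the extra adhesive exposure from NPWT over control is unknown. This stands.
- **Section 6 could be the part in error.** The documents do not confirm that the device contains acrylic adhesive. This also stands, and it determines which section to edit. It does not remove the inconsistency.

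**Conclusion.** The concern holds. As written, a patient with a known acrylic-adhesive allergy who meets the other criteria is eligible and has a 1 in 3 chance of receiving a device that the protocol itself says may provoke a reaction in that patient. The finding about the text needs no assumption. The claim that Section 5b is the part to change assumes that Section 6 describes the device correctly.

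The number of patients concerned is unknown and may be small: at most 0.55 to 5.5 of 110 NPWT patients over the assumed 0.5% to 5% range. The design inputs (25% against a halved rate, 2:1 allocation, 80% power) and the analysis are unaffected. This is a safety inconsistency that should be corrected; it does not threaten the trial's validity.

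**What to change.** In Section 5b, add three words, *or acrylic adhesives*, after the silver criterion. Ask about both allergies in the medical history that Section 5f already schedules. If the device labelling shows no acrylic adhesive, correct Section 6, item 2, and leave Section 5b as it is. If the difference is deliberate, state the reason.

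The cost is one question and a few screen failures, with no added visit or test. Section 5c plans for a "total of 400 patients expected to be consented in order to account for screen failures" and for treatment changes and loss to follow-up as well. Of that allowance of 70, the new exclusion would use at most 2 to 20 over the assumed prevalence range, leaving at least 70 − 20 = 50 for everything else.
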